SAE	Serious Adverse Event/Serious Adverse Experience
SOP	Standard Operating Procedure
US	United States

Protocol Summary

Title	Efficacy of combined nebulized hypertonic saline and chest percussion therapy in acute viral bronchiolitis
Short Title	Combined nebulized hypertonic saline and chest percussion in pediatric bronchiolitis
Brief Summary	This study will examine the efficacy of combined nebulized hypertonic saline with chest percussion therapy in patients age 0 to 24 months admitted to the general inpatient pediatrics unit with acute bronchiolitis. 3% nebulized hypertonic saline treatments combined with 3 minutes of chest percussion therapy will be administered every 6 hours of patients selected for the study.
Phase	N/A
Objectives	Primary outcomes measured will be length of hospital stay and time on supplemental oxygen support, both to be measured in hours. The hypothesis will be that combined nebulized hypertonic saline and chest percussion therapy will decrease length of hospital stay and time on supplemental oxygen support. Secondary outcomes measured will be clinical response (respiratory rate, heart rate, pulse oximetry reading), subjective perceptions of caregivers and health care team, and cost-benefit.
Methodology	Cross-sectional quasi-experimental, open, non-randomized clinical study
Endpoint	Primary endpoints include length of hospital stay and time on supplemental oxygen therapy. Secondary endpoints include trend of respiratory rate, heart rate, and pulse oximetry reading following treatments and subjective perceptions of patients' clinical status based on caregiver and health care team.
Study Duration	12 months
Participant Duration	The duration of participation will begin from time of admission to the general inpatient pediatrics unit until time of discharge from the general inpatient pediatrics unit. This duration may vary from patient to patient, on average will last approximately 1-5 days.
Duration of IP administration	The duration of product administration will begin from time of admission to the general inpatient pediatrics unit until time of discontinuation of supplemental oxygen therapy. This duration may vary from patient to patient, on average will last approximately 1-5 days.
Population	Pediatric patients age 0 to 24 months admitted to the general pediatrics unit admitted for acute bronchiolitis requiring supplemental oxygen therapy
Study Sites	NYU Langone Hospital – Long Island, general inpatient pediatrics unit (NP5)
Number of participants	228
Description of Study Agent/Procedure	
Nebulized 3% hypertonic saline is a solution of 3% sodium chloride delivered via nebulizer and mask and is inhaled by the patient. It is FDA-approved for patients of all ages with sputum production, such as those with acute bronchiolitis.
 
The chest percussion cup is a small, flexible cup made of vinyl that is used to provide gentle chest wall vibrations to assist with airway clearance and is utilized in patients of all ages with sputum production, such as those with acute bronchiolitis.

Reference Therapy	The 2014 American Academy of Pediatrics clinical practice guidelines for management of acute bronchiolitis does not recommend use of nebulized hypertonic saline or chest physiotherapy.
Key Procedures	N/A

Statistical Analysis	
Descriptive statistics (mean \pm standard deviation or median [25th, 75th percentiles] for continuous variables; frequencies and percentages for categorical variables) will be calculated separately by group. The two groups will be compared using the chi-square test or Fisher's exact test, as deemed appropriate, for categorical variables and the two-sample t-test or Mann-Whitney test for continuous data.
 
For all analyses, the standard assumptions of Gaussian residuals and quality of variance will be tested. If the standard assumptions are not met, a transformation will be performed (i.e. logarithm transformation). Results will be brought back to the original units and reported as geometric means with their corresponding lower and upper confidence limits.
 
For the assessment of number of days on supplemental oxygen therapy (i.e. count data), a Poisson, Negative Binomial (NB), Zero-Inflated Poisson (ZIP), or Zero-Inflated Negative Binomial (ZINB) model will be used.
 
A result will be considered statistically significant at the $p < 0.05$ level of significance. All analyses will be performed using SAS version 9.4 (SAS Institute Inc., Cary, NC).

----------------------	---

SCHEMATIC OF STUDY DESIGN

1 Key Roles

[name], DO, principal investigator
NYU Langone Hospital – Long Island
Department of Pediatrics
[name]
[contact]
[contact]

Sub-investigators:

[name].
[name].
[name].
[name].
[name], D.O.

The sub-investigators are pediatric medical residents with competent knowledge in the background and relevant literature of acute bronchiolitis and the standards of care. They have had experience in interaction with this patient population and have demonstrated competence in pediatric physician milestones. All physicians listed as sub-investigators have experience in clinical research and obtaining consent, maintaining confidentiality, as well as experience with safe data handling. Per the residency program and New York State requirements, pediatric residents are not required to obtain a state medical license during their training, thus the listed sub-investigators do not have a New York State medical license number.

This study currently does not have an identified biostatistician due to no biostatistician available at NYU Langone Hospital – Long Island. A data analysis plan has been developed. Once enrollment begins, data collection will occur, but this data will not be analyzed until a biostatistician has been identified and added to this study. A biostatistician will be added at the earliest time possible pending NYU Langone Hospital – Long Island and NYU Grossman Long Island School of Medicine's administration and the biostatistic department's process on filling this position.

2 Introduction, Background Information and Scientific Rationale

2.1 Background Information and Relevant Literature

Acute bronchiolitis is a viral infection of the lower respiratory tract that primarily involves infants and young children and is only present in the pediatric population. It is the most common cause of hospitalizations in resource-rich countries. Bronchiolitis can be caused by a number of viruses, the most common being respiratory syncytial virus (RSV). [1] In the Northern Hemisphere, viral infections resulting in acute bronchiolitis increase beginning late October and will peak during the winter months of January and February and will decline through April. [2]

Bronchiolitis leads to airway inflammation, edema, and increased production of mucus. Causative viruses are spread via direct contact and inoculation at nasal mucosa or from inhalation of infective respiratory droplets. The viruses replicate in the nasopharyngeal airway and following a 4 to 6-day incubation period after transmission, the initial upper respiratory tract infection symptoms appear. Subsequent respiratory tract epithelial cell injury and necrosis occurs and this debris is aspirated into the lower respiratory tract, resulting in further inflammation, edema, and necrosis of the bronchioles, leading to airway narrowing and obstruction that is classic for acute bronchiolitis. [3]

The diagnosis of acute viral bronchiolitis is clinical, although use of molecular detection tests may help identify the causative organism. Infants and young children with acute bronchiolitis begin with upper airway symptoms of congestion, cough, and rhinorrhea that may progress to signs and symptoms of respiratory distress due to resultant lower respiratory tract obstruction such as tachypnea, accessory respiratory muscle use known as retractions, nasal flaring, grunting, or wheezing, and may also exhibit low oxygen saturations. [2] It is the resultant symptoms of lower respiratory tract obstruction that often lead to infants and young children with acute viral bronchiolitis to present to the emergency department and subsequently be admitted to the hospital.

The American Academy of Pediatrics (AAP) published guidelines in 2014 to help guide pediatricians in management of pediatrics patients with acute bronchiolitis. The strongest recommendations lie in supportive management measures, including oxygen supplementation, intravenous fluids if needed, and suctioning of the nose and/or mouth to relieve congestion. The AAP currently recommends against other treatments such as albuterol, antibiotics, steroids, saline nebulization, or chest physiotherapy, citing little to no significant efficacy of these treatment regimens. Over the years, there have been emerging studies investigating the use of these treatments and there has been some evidence demonstrating benefit in using nebulized saline treatments. Because of the non-invasiveness and low side effect profiles of nebulized hypertonic saline breathing treatments and chest percussion therapy, and their potential of improving severity of symptoms in children with acute viral bronchiolitis, it is reasonable to investigate treatment regimens that are outside the bounds of the current clinical practice guidelines, and this study intends combine these two treatments to investigate their efficacy as a combined treatment regimen for acute viral bronchiolitis.

2.2 Name and Description of the Investigational Agent

Nebulized 3% hypertonic saline is an inhaled respiratory solution composed of sodium chloride. It is dispensed as single 4 milliliter vials that are sterile, preservative-free, and non-pyrogenic. It is administered through a nebulizer via mask or inhalation tube apparatus. It is FDA-approved for patients of all ages with sputum production, such as those with acute bronchiolitis. However, there is no specific labeled use of this medication for pediatric patients with acute bronchiolitis.

The chest percussion cup is a commercially-available device used for chest physiotherapy. It is made of vinyl and shaped like a cup with an open end that provides percussion and a handle on the other end. It is utilized by gentle and repeated motions of percussion on the chest wall to create chest wall vibrations to induce airway clearance and is used in patients of all ages with sputum production, such as those with acute bronchiolitis. However, there is no specific labeled use of this device for pediatric patients with acute bronchiolitis.

2.2.1 Clinical Data to Date

Hypertonic saline nebulization

Hypertonic saline nebulization is one of the adjuvant therapies that has been used for management of acute viral bronchiolitis. Theories behind its efficacy lie within the proposed effects of airway hydration and reduction of edema as well as mucus clearance. [1] A 2017 Cochrane systematic review showed that patients with acute bronchiolitis who received hypertonic saline nebulization treatments had a significantly shorter length of stay in comparison with patients who received normal saline nebulization treatments. This shows that there may be some benefit in using hypertonic saline nebulization in the management of acute bronchiolitis. The review however did show a low quality in evidence as well as large variations between studies. [5] The 2014 American Academy of Pediatrics clinical practice guidelines has a moderate recommendation against the use of hypertonic saline nebulization in treatment for acute bronchiolitis, with the notion that new information may arise as further evidence on this treatment option emerges. [4] Because of the limited evidence and low quality of studies, the need for standardized and multi-centered studies remains in regards to the use of hypertonic saline nebulization in acute bronchiolitis.

The side effect profile of hypertonic saline nebulization treatments remains low. There is some concern with treatments causing bronchospasm, but a retrospective cohort studied showed a 0.3% rate of occurrence of this side effect. The concern for bronchospasm seems to increase with the increase in concentration of hypertonic saline nebulization treatments, as formulations range from 3% to 7%. Other adverse events were reported in this study and showed a 1.0% rate of occurrence, and these events involved excessive coughing, which was transient. [6] Other side effects that have been reported such as hypernatremia, desaturation, bradycardia, vomiting and diarrhea were minor and spontaneously resolved. [5]

Given the evidence of potential benefits of nebulized hypertonic saline in improvement of airway hydration, edema and clearance in conjunction with a very low side effect profile, its use in a study to determine its efficacy is justifiable.

Chest percussion therapy

Chest physiotherapy is a group of airway clearance techniques that may assist with clearance of mucus. These techniques include chest vibration or percussion, assisted coughing devices, and forced expiratory techniques.

A non-invasive and gentle chest physiotherapy device that can be used in pediatric patients such as those in the age group for this study is a chest percussion cup. The chest percussion cup is usually made of vinyl and shaped like a suction cup with a small handle on the closed end. The technique involves tapping/percussion of the chest with this cup to cause vibration of the chest wall. The theory behind this technique is that it will loosen mucus trapped in the lower respiratory tract and allow for ease of expectoration and airway clearance. This method has been used in treatment for acute bronchiolitis given the pathophysiology of mucus build-up and debris in the lower respiratory tract of patients with acute bronchiolitis who are often have difficulty clearing this mucus. [7]

In a systematic review evaluating the effects of airway clearance techniques in treatment for acute bronchiolitis, while concluding that respiratory therapy techniques such as chest percussion did not reduce the severity of the disease, the review did note that there were newer studies with positive results that had not been included. Furthermore, several studies in this review showed several positive outcomes, such as improvement in clinical scores, positive perception from caregivers on patients' clinical status, and improved oxygen saturation. One study also found that there was a noted decreased length of stay in patients with moderate disease. [8] However, due to the heterogeneity of these studies the use of chest physiotherapy in acute bronchiolitis remains controversial and need for further randomized controlled trials remains.

In regards to the side effect profile of chest percussion therapy, adverse effects of concern include excessive coughing and irritability. There were two case reports of rib fractures in children who received chest physiotherapy; however these were related to the more invasive forced expiratory techniques. Overall, the evidence lacked any statistically significant adverse outcomes following use of chest percussion therapy in children. [7] It can be concluded that chest percussion therapy is the least invasive of the chest physiotherapy techniques and the potential adverse effects of chest percussion therapy remain very low.

2.2.2 Dose Rationale

The dose for nebulized 3% hypertonic saline is a 1 vial (4 milliliters) every six hours. The timing of nebulized hypertonic saline is discussed in a Cochrane systematic review conducted for patients with cystic fibrosis, where the review concluded that hypertonic saline nebulization treatments every 6 hours may maximized airway clearance and perceived effectiveness.[9] Rationale for dosing in acute bronchiolitis was not found in literature for this dosing.

The frequency of chest percussion therapy with a chest percussion cup will be every six hours to pair with nebulized treatments. Chest percussion therapy will be provided for 3 minutes. There is currently no rationale available in literature for this dosing or duration.

2.3 Rationale

Over the years, many different interventions have been trialed for bronchiolitis, including antibiotics, glucocorticoids, antivirals, nebulized treatments, positive end-expiratory pressure respiratory support, and chest physiotherapy. The American Academy of Pediatrics published clinical practice guidelines for the diagnosis and management of acute viral bronchiolitis in 2014 which recommended minimal interventions and mainly focuses on hydration and oxygenation and did not recommend use of such interventions listed previously. [4] Despite these published guidelines, there remains a discordance and inconsistency in the care and management of patients admitted to pediatric units for acute viral bronchiolitis. Furthermore, there are some newer studies and evidence finding some value in a few of these interventions while other studies continue to lack evidence in the value of these interventions.

2.4 Potential Risks & Benefits

2.4.1 Known Potential Risks

The side effect profile of hypertonic saline nebulization treatments remains low. There is some concern with treatments causing bronchospasm, but a retrospective cohort studied showed a 0.3% rate of occurrence of this side effect. The concern for bronchospasm seems to increase with the increase in concentration of hypertonic saline nebulization treatments, as formulations range from 3% to 7%. Other adverse events were reported in this study and showed a 1.0% rate of occurrence, and these events involved excessive coughing, which was transient. [6] Other side effects that have been reported such as hypernatremia, desaturation, bradycardia, vomiting and diarrhea were minor and spontaneously resolved. [5] There are no long-term risks associated with nebulized hypertonic saline and it is considered safe and inexpensive.

The side effect profile of chest percussion therapy, adverse effects of concern include excessive coughing and irritability. There were two case reports of rib fractures in children who received chest physiotherapy; however these were related to the more invasive forced expiratory techniques. Overall, the evidence lacked any statistically significant adverse outcomes following use of chest percussion therapy in children. [7] It can be concluded that chest percussion therapy is the least invasive of the chest physiotherapy techniques and the potential adverse effects of chest percussion therapy remain low.

There are no foreseeable physical, psychological, social, legal, or economic risks to participants by virtue of participation in this study. The value of information to be gained from this study may further guide clinicians on a more evidence-based approach to treatment of acute bronchiolitis in pediatric patients.

Because the study involves pediatrics, it is considered a study on a vulnerable population. There are no additional risks than those described previously.

Minimizing Risks

Because the study involves pediatrics, it is considered a study on a vulnerable population. There are no additional risks than those described previously.

Standard of care monitoring will be conducted for all study participants to minimize risk. This will include routine monitoring vital signs every 4 hours and routine care team monitoring from physician providers and nurses. As with all patients admitted to the general inpatient pediatrics unit, the call bell will always be within reach for the parents or legal guardians caring for the child, and whenever they have any concerns or questions, they are oriented to use the call bell to alert the care team. Respiratory therapists will be present while providing treatments and will alert the care team of any concerns or noted adverse events. Because of the low side effect profile of both nebulized 3% hypertonic saline and chest percussion therapy, these measures are deemed sufficient to minimize risks to subjects.

2.4.2 Known Potential Benefits

The potential benefits of nebulized 3% hypertonic saline treatments is improved airway clearance. A 2017 Cochrane systematic review showed that patients with acute bronchiolitis who received hypertonic saline nebulization treatments had a significantly shorter length of stay in comparison with patients who received normal saline nebulization treatments. This shows that there may be some benefit in using hypertonic saline nebulization in the management of acute bronchiolitis. [5]

The potential benefit of chest percussion therapy is improved airway clearance. Several studies in this review showed several positive outcomes, such as improvement in clinical scores, positive perception from caregivers on patients' clinical status, and improved oxygen saturation. One study also found that there was a noted decreased length of stay in patients with moderate disease. [8].

3 Objectives and Purpose

3.1 Primary Objective

The primary objectives of this study of nebulized 3% hypertonic saline treatments combined with chest percussion therapy in treatment of acute bronchiolitis in pediatric patients age 0 to 24 months admitted to the general inpatient pediatrics unit is to assess their efficacy on length of hospital stay and time on supplemental oxygen therapy.

3.2 Secondary Objectives

The secondary objectives of this study of nebulized 3% hypertonic saline treatments combined with chest percussion therapy in treatment of acute bronchiolitis in pediatric patients at 0 to 24 months admitted to the general inpatient pediatrics unit is to assess their efficacy on disease severity and subjective perceptions on effectiveness.

4 Study Design and Endpoints

4.1 Description of Study Design

Groups:

1. Control group: Patients meeting criteria as above prior to start date, beginning 12 months prior to start date of study, will be examined via retrospective chart review

2. Experimental group: All patients meeting criteria as above beginning start date of study will be enrolled in study to receive adjuvant therapy with 3% hypertonic saline nebulization treatments combined with 3 minutes of chest physiotherapy.

Statistical Methods:

Descriptive statistics (mean \pm standard deviation or median [25th, 75th percentiles] for continuous variables; frequencies and percentages for categorical variables) will be calculated separately by group. The two groups will be compared using the chi-square test or Fisher's exact test, as deemed appropriate, for categorical variables and the two-sample t-test or Mann-Whitney test for continuous data.

For all analyses, the standard assumptions of Gaussian residuals and quality of variance will be tested. If the standard assumptions are not met, a transformation will be performed (i.e. logarithm transformation). Results will be brought back to the original units and reported as geometric means with their corresponding lower and upper confidence limits.

For the assessment of number of days on supplemental oxygen therapy (i.e. count data), a Poisson, Negative Binomial (NB), Zero-Inflated Poisson (ZIP), or Zero-Inflated Negative Binomial (ZINB) model will be used.

A result will be considered statistically significant at the $p < 0.05$ level of significance. All analyses will be performed using SAS version 9.4 (SAS Institute Inc., Cary, NC).

Sample Size Considerations:

The proposed sample size for this study is 228 subjects ($n=114$ per group). Based on data published by Gajdos, et al., the mean duration of hospitalization for bronchiolitis recorded in the study hospitals during previous years was 6.5 days and standard deviation = 3.5 days. For a type I error of 0.05 and a power of 0.80, for detecting a 20% decrease in duration of hospitalization, a total of 228 subjects would be included (114 subjects in each group).

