5.6 Total Number of Participants and Sites

Recruitment will end when approximately 114 participants are enrolled. It is expected that approximately 200 participants will be enrolled in order to produce 114 evaluable participants.

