10.3 Analysis Datasets

Control group: Patients meeting criteria as above prior to start date, beginning 12 months prior to start date of study, will be examined via retrospective chart review.

Experimental group: All patients meeting criteria as above beginning start date of study will be enrolled in study to receive adjuvant therapy with 3% hypertonic saline nebulization treatments combined with 3 minutes of chest physiotherapy.

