10.5 Sample Size

The proposed sample size for this study is 228 subjects ($n=114$ per group). Based on data published by Gajdos, et al., the mean duration of hospitalization for bronchiolitis recorded in the study hospitals during previous years was 6.5 days and standard deviation = 3.5 days. For a type I error of 0.05 and a power of 0.80, for detecting a 20% decrease in duration of hospitalization, a total of 228 subjects would be included (114 subjects in each group).

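### No rule links the 12-month control window to the planned 114 controls, so chart selection is open to outcome or season; using every eligible chart from matching months would close the gap

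*Combined protocol and SAP*

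**What the plan says.** Section 4.1 says that control patients, "beginning 12 months prior to start date of study, will be examined via retrospective chart review". Section 10.3 (Analysis Datasets) repeats this control definition: "Control group: Patients meeting criteria as above prior to start date, beginning 12 months prior to start date of study". Neither section mentions sampling, ordering, matching or a maximum. For the other arm, section 4.1 is explicit that everyone eligible is taken: "Experimental group: All patients meeting criteria as above beginning start date of study will be enrolled in study". The word for all is absent from the control definition.

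Section 10.5 gives a number: "The proposed sample size for this study is 228 subjects", split as 114 per group. Section 4.1 and section 10.4.7.2 repeat this, and the Protocol Summary lists 228 participants.

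On timing, section 5.6 states: "Recruitment will end when approximately 114 participants are enrolled". The Protocol Summary gives a study duration of 12 months. Section 2.1 describes case numbers that rise from late October, "will peak during the winter months of January and February and will decline through April". Section 10.6 says that the study is not blinded and uses neither masking nor randomization.

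**The concern.** A date window defines one set of controls and a target number may define another. They agree only if exactly 114 charts qualify. If more qualify, someone has to decide whether to use them all or which to keep, and the plan gives no basis for that decision.

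This matters more here than in a prospective arm. A control child's stay is over when the chart is opened, so length of stay and oxygen time, the two primary endpoints, can be seen while eligibility is being judged. Some exclusions in section 5.2 call for judgement, since the lists of respiratory conditions are open-ended. Selection related to length of stay would shift the control mean, and the unadjusted tests in section 10.4.1 would not detect it. No log of screened control charts is required, so a reader could not check afterwards how the group was formed.

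Season is a second route. The control window is always 12 months, but experimental accrual stops at a count. If 114 children are reached early, a full-year control group is compared with a part-year treated group. Filling the control group in date order until 114 are found could also give it a different mix of months.

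**Working it through.** **Inputs.** Section 10.5 gives the mean and standard deviation of stay, "during previous years was 6.5 days and standard deviation = 3.5 days", with type I error 0.05, power 0.80 and a 20% decrease. The target difference is 0.20 × 6.5 = 1.3 days. Sidedness is not stated.

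**The plan's own figure.** Two-sided, normal approximation:

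n per group = 2 × (1.960 + 0.842)² × 3.5² / 1.3² = 113.8, so 114.

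The stated 114 per group, 228 in total, reproduces. A one-sided test would need 90.

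**Power if all eligible charts are used.** Hold the experimental arm at 114 and let m be the number of controls. The documents do not give m, so the values below are assumptions. For scale, section 5.4 expects about 200 children screened to reach 114 in the experimental arm, while sections 5.6 and 10.6 expect about 200 enrolled. Neither figure counts control charts.

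SE = 3.5 × √(1/114 + 1/m); power = Φ(1.3/SE − 1.960); difference detectable at 80% power = (1.960 + 0.842) × SE.

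| Controls m | SE (days) | Power | Detectable difference (days) |
|---|---|---|---|
| 80 | 0.511 | 0.721 | 1.43 |
| 100 | 0.480 | 0.774 | 1.34 |
| 114 | 0.464 | 0.801 | 1.30 |
| 150 | 0.435 | 0.848 | 1.22 |
| 200 | 0.411 | 0.886 | 1.15 |

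The noncentral t gives slightly lower power: 0.717, 0.770, 0.797, 0.846 and 0.884.

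**How far selection could shift the result.** This simulation is illustrative, and its inputs are assumptions. Stay is lognormal with mean 6.5 and SD 3.5, there is no true effect, and 114 controls are picked from M eligible charts. The correlation ρ is between log stay and the latent score that ranks charts for picking. A positive ρ favours longer stays among the controls, which flatters the treatment; a negative ρ would work the other way.

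| ρ | Shift in control mean, M = 150 (days) | Type I error | Shift in control mean, M = 200 (days) | Type I error |
|---|---|---|---|---|
| 0 | about 0 | 0.05 | about 0 | 0.05 |
| 0.1 | +0.14 | 0.06 | +0.22 | 0.07 |
| 0.2 | +0.26 | 0.08 | +0.45 | 0.15 |
| 0.3 | +0.38 | 0.14 | +0.66 | 0.28 |

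The first row shows that a limit of 114 does no harm in itself if picking is unrelated to stay. Any harm comes from how charts are picked.

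**Season.** The documents give no monthly admission counts and no length of stay by month, so the effect of unequal months cannot be sized.

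**The case against.** The strongest reply is that the plan has no cap to begin with. Section 10.3 defines the control dataset by dates alone, 114 is described as a proposed size from a power calculation, and the only stopping rule tied to 114 concerns recruitment, which does not apply to charts. On that reading every eligible chart is used. This is a fair reading, and it rules out saying that the control group is fixed at 114. It does not settle the matter, because section 10.5 still states 114 in each group and no section says which statement governs.

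A reader might go further and infer that eligible charts must be discarded. The documents do not support that. They give no count, and the exclusions for bronchodilators, antibiotics, antivirals, steroids and diuretics could leave 114 or fewer. A reader might also infer that unblinded investigators will choose charts with the outcome in view. No section says who abstracts the control charts; section 13.5 refers only to trial staff at the site under the principal investigator's supervision. Outcome-aware selection is left open, not described.

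On season, the planned study duration equals the control window, so if accrual takes the full 12 months the two groups span the same seasons. The mismatch arises only if recruitment closes early, which section 5.6 allows.

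Finally, extra controls tighten the interval around an estimate that may still be confounded. That is correct: the gain is in precision and in a reproducible control group, not in comparability between years.

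**Conclusion.** The gap is real: there is a 12-month control window, a planned control group of 114 and no rule joining them, in an unmasked study whose control outcomes are already recorded. Bias is a risk and not a demonstrated result. It needs more than 114 eligible charts with selection related to stay, or different months in the two groups. The documents establish neither, and prevent neither.

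The precision at stake is moderate. With 114 treated children and the plan's SD of 3.5 days, power for 1.3 days rises from about 0.80 to about 0.85 with 150 controls and 0.89 with 200, and falls to about 0.77 with 100. The chart counts are assumptions. The stated sample size is not an arithmetic error. The case for acting is that the remedy is cheap and must be in place before any chart is opened.

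**What to change.** In sections 4.1, 10.3 and 10.5:

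- Define the control group as every eligible chart admitted before the study start date in the same calendar months as the experimental accrual, or the full 12 months if accrual takes 12 months or longer. No control admission then falls after study start. State that there is no cap at 114.
- Decide eligibility from admission-time and treatment-exclusion fields before discharge time and oxygen stop time are viewed.
- Keep a log of all screened charts with the reason for each exclusion.
- Restate the planned size as 114 experimental children and all eligible controls, and bring the 228 in the Protocol Summary and section 10.4.7.2 into line. Say what follows for power if fewer than 114 charts qualify.

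The cost is protocol wording and the time to abstract the extra charts: about 36 more than 114 if 150 qualify, or 86 more if 200 do. No further enrolment is needed. The change does not remove the confounding of a historical comparison, which has to be addressed separately.
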